7.2.6. User Experience

Colonoscopists using the EVA-C System as a part of this study may be asked to provide their written or electronic feedback about their experiences with using this system throughout the course of the study.

7.2.7. Investigational Product

The study device will be used on the day of the study visit. The investigator is responsible for accountability at the study site as indicated in Section 11.3, and the study devices will be stored in a locked cabinet and/or in a locked office at the site.

7.2.8. Adverse Events

Adverse events related to study device and study procedures, all serious adverse events, and all unanticipated adverse device effects will be reported on the appropriate CRF in a timely manner as indicated in Section 9. They will be collected from time of consent to study exit and will be reviewed by the Sponsor. The investigator will provide further information regarding adverse events as requested by the Sponsor.

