7.2.3. Randomization/Blinding/Masking

Enrolled subjects will be randomized into control or intervention arms in a 1:1 allocation using block randomization within subjects strata defined by age-group, sex, and risk-group. Subjects will be assigned to control or intervention arms within each colonoscopist based on a predetermined randomization schedule.

Subjects, investigators, study site personnel, and pathologists will not be blinded to treatment assignments. All Verily personnel involved in the statistical analysis of this study will be blinded to treatment assignment. For the interim analysis, unblinded analysis will be performed by an independent statistician, the results of which will be communicated to a select group of Verily personnel not involved in the study management.

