7.2.5. Visit Schedule

After confirmation that the ICF has been signed by both the investigator (or designee) and the subject and eligibility has been confirmed, the following assessments will be performed.

- Subjects will be randomized using the randomization system within the EDC system provided by Sponsor.
- If a subject is assigned to the intervention group, the EVA-C System will be turned on prior to scope insertion and will remain on for the duration of the colonoscopy.
- If a subject is assigned to the control group, the EVA-C System will not be used and will remain turned off during the colonoscopy.
- In both the control and intervention groups, the colonoscopy video feed will be recorded from scope-in to scope-out, while the scope is inside the subject. Any

protected health information (PHI) in the colonoscopy video feed will be masked prior to recording or removed after recording, but prior to sending to Sponsor.

Colonoscopy procedure

- High Definition White Light Endoscopy will be used, per standard of care.
- Dye-based or virtual chromoendoscopy may be used for characterizing individual polyps at the colonoscopist's discretion, but may not be used for overall inspection of the colon.
- Bowel preparation will be evaluated after cleaning and will be scored using the Boston Bowel Preparation Scale (BBPS) separately in each of the three regions of the colon: the right colon (including the cecum and ascending colon), the transverse colon (including the hepatic and splenic flexures), and the left colon (including the descending colon, sigmoid colon, and rectum).¹ Subjects with a BBPS score of 0 or 1 in any of the three colonic regions of the colon will be excluded from the Per Protocol analysis.
- In the right, transverse, and left colon, lesions are to be removed, at the colonoscopist's discretion, per standard of care. Notably, in the left colon, only those lesions that appear adenomatous are to be removed, per standard of care.

In the intervention arm only:

System is not intended to change the colonoscopist's management of an identified polyp or lesion.

- The colonoscopist is expected to interrogate any region of interest highlighted by the EVA-C System bounding box.

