7.2.9. Protocol Deviations

A protocol deviation is when the procedures that are outlined in the Protocol are not followed. There are two types of protocol deviations in this study: major deviations and minor deviations.

A major deviation is defined as an event that resulted in an increased risk to a subject or others; affecting the rights, safety and/or welfare of the subject; or affecting the integrity of the clinical study. Major deviations include (but are not limited to): failure to obtain Informed Consent prior to enrollment, enrolled subject who participated in the study session does not meet inclusion/exclusion criteria or unauthorized use of study device on a subject not enrolled in the study; AEs that are not reported by the Investigator during the protocol-specified timeframe.

A minor protocol deviation is defined as deviating from the protocol and include (but are not limited to): protocol-required testing and/or study visit were not completed.

All deviations will be reported on the appropriate CRF.

7.3. **Test Procedures**

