8.3. Risks

This study is a non-significant risk device study, and this study exposes subjects to minimal risks not expected to be significantly different from patients' routinely scheduled colonoscopy visit.

Possible risk, in addition to risks associated with the clinical colonoscopy, may include:

- Algorithm malfunction or misinterpretation leading to:
 - False positive detection potentially resulting in procedural delays due to prolonged interrogation/examination. However, the software is not designed to replace clinical decision making.
 - False negative missed detection, potentially resulting in delayed patient treatment. However, this delay would have occurred regardless of device use. Additionally, it is possible physicians could develop an overreliance on the device.
- Failure to identify lesions, potentially resulting in delayed patient treatment, because of software or hardware malfunction. Such malfunctions might include:
 - Incompatibility with hardware and/or data source
 - Inadequate mapping of software architecture
 - Degradation of image quality
 - Prolonged delay of real-time endoscopic video

In all cases of device malfunction, the device may be turned off or unplugged by the colonoscopist or the study team at any time, to avoid further procedural risk, and the procedure would continue as planned without the use of the EVA-C System.

Another risk of this study includes breach of privacy and confidentiality of protected health information (PHI).

The following measures will be implemented to help minimize risks to subjects during the study:

• All PHI will be stored in a secure locked office on a password protected computer. The informed consent forms will be stored in a locked cabinet in a locked office at the site. Measures to ensure complete de-identification prior to data transfer and analysis will be taken.

9. Adverse Events (AE), Serious Adverse Events (SAE), and Unanticipated Problems

During and following a subject's participation in the study, the investigator/institution should ensure that adequate medical care is provided to a subject for any adverse events, including clinically significant laboratory values, related to the trial. The investigator/institution should inform a subject when medical care is needed for intercurrent illness(es) of which the investigator becomes aware.

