9.1. Adverse Events

An Adverse Event (AE) is defined as any untoward medical occurrence, unintended disease or injury in subjects, users or other persons, that is considered a change from baseline or pre-study status, whether or not related to the investigational medical device.

Any pre-existing medical condition or symptoms present in a subject will not be considered an AE in this study, unless it worsens as a result of this study.

For this study, AEs related to the study device and study procedures will be reported on an AE Case Report Form and will include the following: Date/time of onset, date the site first becomes aware of the event, description of the event, the duration of the event, the severity of the event, assessment of the relation of the event to the study device and study procedure, description of action taken, if any, and the event outcome.

In the event medical care to a subject is required, the medical care given to, and medical decisions made on behalf of, subjects should always be the responsibility of a qualified physician.

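### Non-serious adverse events reach the form only if judged related by staff who know the arm, so a by-arm comparison of them could be distorted in either direction (minor)

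*Combined protocol and SAP*

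**What the plan says.** Section 9.1 defines an adverse event broadly, "whether or not related to the investigational medical device". It then narrows what is written down in this study: "AEs related to the study device and study procedures will be reported on an AE Case Report Form". Section 7.2.8 gives the same scope and exempts only serious events and unanticipated device effects: "Adverse events related to study device and study procedures, all serious adverse events, and all unanticipated adverse device effects will be reported". One of the items on that form is an "assessment of the relation of the event to the study device and study procedure".

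On who knows the arm, section 7.2.3 states: "Subjects, investigators, study site personnel, and pathologists will not be blinded to treatment assignments". For a control subject, section 7.2.5 says that "the EVA-C System will not be used and will remain turned off during the colonoscopy".

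Two places bear on whether the colonoscopy is a study procedure. The schedule table in section 7.1 lists it for both arms, along with adverse event evaluation. Section 8.3 introduces the study's own risks with the words "Possible risk, in addition to risks associated with the clinical colonoscopy, may include", which sets the risks of the clinical colonoscopy to one side.

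**The concern.** The rule makes relatedness a condition of entry, when it could be a fact recorded about every event. The people applying it know the arm, and the device limb of the condition can be met in one arm only. Two identical minor events, one per arm, could therefore be treated differently.

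What is at stake is the descriptive safety comparison. The device is meant to raise detection and hence excisions, so more minor procedural events in the intervention arm would be the natural safety counterpart. Sections 8 and 8.3 say the risk should not differ from that of a routine colonoscopy. A table built from filtered events is a weak check on that statement, and an event that was never recorded cannot be restored at analysis.

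The point covers non-serious events only. The definition of a serious event and the length of the collection period are separate matters.

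**Working it through.** The plan states no AE rate, so there is no figure to reproduce. The check is mainly a reading of the text, followed by one illustration.

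**1. What reaches the form.** Sections 7.2.8 and 9.1 agree: serious events and unanticipated device effects always do; a non-serious event does only if related to the device or study procedures. I read the rule as either of the two. Requiring both would exclude every control-arm event, although section 7.1 schedules AE evaluation in both arms.

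**2. Who judges.** Section 9.1 names no assessor. Section 7.2.9 lists as a major deviation "AEs that are not reported by the Investigator during the protocol-specified timeframe", so the investigator is the reporter and probably also assesses relatedness. That is an inference, but it matters little, because section 7.2.3 leaves all site staff unblinded.

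**3. Routes onto the form, by arm.**
- Intervention: related to the device, or related to a study procedure.
- Control: related to a study procedure only, since the device is off (section 7.2.5).

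For control subjects everything turns on whether the clinically indicated colonoscopy is a study procedure. Section 7.1 suggests that it is; section 8.3 sets its risks apart; no section settles it.

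**4. Later checks.** Section 9.3 gives the Medical Monitor serious and unanticipated effects only. Sponsor review under section 7.2.8 covers events already collected. No blinded assessment or adjudication of non-serious events is described.

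**5. Illustration.** All rates and shares here are assumptions. Let p be the true rate in an arm and q the share of events judged related.

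Recorded rate = p × q, so the recorded ratio (intervention/control) = (p_I / p_C) × (q_I / q_C). When true rates are equal this reduces to q_I / q_C.

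Take p = 5% in both arms and 600 per arm (section 13), that is 600 × 0.05 = 30 true events per arm.

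| | Share judged related | Recorded rate | Recorded events |
|---|---|---|---|
| Control | 50% | 0.05 × 0.50 = 2.5% | 15 |
| Intervention, low | 60% | 0.05 × 0.60 = 3.0% | 18 |
| Intervention, high | 80% | 0.05 × 0.80 = 4.0% | 24 |

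The recorded ratio is 3.0/2.5 = 1.2 to 4.0/2.5 = 1.6, with no true difference. Exchange the shares between arms and it is 2.5/3.0 = 0.83 to 2.5/4.0 = 0.63. With equal shares it is 1.0 and nothing is distorted.

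**The case against.** The case for leaving the rule alone is substantial.

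- **It is a deliberate, open choice.** The scope is stated consistently in two sections of a study classed as non-significant risk. A reader might call the broad definition and the narrow reporting rule contradictory. They are not: section 9.1 defines a term and then says which events this study will report.
- **Colonoscopy is probably a study procedure in both arms.** That is the more natural reading of section 7.1, and section 8.3 does not set the reporting rule. This stands, but it leaves the matter to inference at each site.
- **There is little time for unrelated events.** The protocol summary puts participation at about 1-2 hours without follow-up. This keeps the numbers small. However, most events in that window would arise from the clinical colonoscopy, which is the class whose status is unclear.
- **No outcome that drives the trial's conclusion is touched.** Sections 5.3, 5.4 and 13 list no AE endpoint and no between-arm AE test. A reader might infer a threat to the APC or PPA result, or an inflated false-positive rate. Neither follows: the co-primaries do not use AE data, and there is no AE test whose error rate could be inflated.
- **A loss of power to detect real harm cannot be claimed.** A reader might infer one, but its direction depends on which events are dropped. Assume a true 3% v 6% at 600 per arm. The unpooled normal approximation gives SE = √[(0.03×0.97 + 0.06×0.94)/600] = 0.0119, z = 0.03/0.0119 = 2.51, and power Φ(2.51 − 1.96) = 71%. Dropping half of all events evenly gives 1.5% v 3.0% and 42%. Keeping the 3-point excess, as a relatedness rule should, and half the background gives 1.5% v 4.5% and 86%. The documents do not say which applies.
- **Recording everything would not remove open-label bias.** Unblinded staff would still decide what to note as an AE. This stands as a limit on the fix.

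**Conclusion.** The concern holds as a minor one. The text of sections 7.2.8 and 9.1 applies a relatedness filter to non-serious events, operated by staff who know the arm. One of its two limbs is available in the intervention arm only, and the scope of the other is not stated outright. Any descriptive by-arm comparison of these events could therefore be distorted in either direction.

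The documents establish that this could happen, not that it will, and they contain nothing from which to size it. The 2.5% v 3.0-4.0% example rests wholly on an assumed true rate of 5% and assumed shares of 50% v 60-80%. It shows the mechanism and is not an estimate. That the investigator assesses relatedness is inferred; that everyone at the site is unblinded is stated.

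**What to change.** In sections 7.2.8 and 9.1, record every AE in both arms from consent to study exit, which is the existing window, whatever its relation to the device or procedure. Keep relatedness as the form field it already is. Tabulate AEs by arm regardless of relatedness, with the related subset as a second table.

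If the sponsor prefers the narrower collection, the minimum is to define study procedures identically for both arms, saying expressly whether the clinically indicated colonoscopy is included, and to make no comparative claim on non-serious AE rates.

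The cost is wording in the protocol and the CRF guidelines, plus a few extra AE forms, some for unrelated events. Endpoints, sample size and analysis of the co-primaries do not change.

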7.2.9. Protocol Deviations

A protocol deviation is when the procedures that are outlined in the Protocol are not followed. There are two types of protocol deviations in this study: major deviations and minor deviations.

A major deviation is defined as an event that resulted in an increased risk to a subject or others; affecting the rights, safety and/or welfare of the subject; or affecting the integrity of the clinical study. Major deviations include (but are not limited to): failure to obtain Informed Consent prior to enrollment, enrolled subject who participated in the study session does not meet inclusion/exclusion criteria or unauthorized use of study device on a subject not enrolled in the study; AEs that are not reported by the Investigator during the protocol-specified timeframe.

A minor protocol deviation is defined as deviating from the protocol and include (but are not limited to): protocol-required testing and/or study visit were not completed.

All deviations will be reported on the appropriate CRF.

7.3. **Test Procedures**

7.3.1. Laboratory parameters

This section is not applicable for this study.

7.3.2. Special Methodologies and Evaluations

7.3.2.1. **Retrospective Review of Colonoscopy Video Recording**

Inspection time, defined as time when not resecting, washing, or preparing for resection, will be calculated retrospectively from colonoscopy video recording (subtracting out the non-inspection time).

8. Risk Analysis

This study is a non-significant risk device study and subjects in this study will not be exposed to significant risk. The risks of participation in this study are not expected to be different from patients' routinely scheduled colonoscopy visit.

8.1. Risk Analysis

Verily Life Sciences has conducted an analysis of the benefits and risks of the EVA-C System.

Verily Life Sciences has determined that this clinical investigation is justified, as the overall potential benefit to the population outweighs its risks.

8.2. Benefits

There is no direct benefit to the participating subjects for this study, but the information obtained will be used in scientific research and may be helpful to others in the future.

8.3. Risks

This study is a non-significant risk device study, and this study exposes subjects to minimal risks not expected to be significantly different from patients' routinely scheduled colonoscopy visit.

Possible risk, in addition to risks associated with the clinical colonoscopy, may include:

- Algorithm malfunction or misinterpretation leading to:
 - False positive detection potentially resulting in procedural delays due to prolonged interrogation/examination. However, the software is not designed to replace clinical decision making.
 - False negative missed detection, potentially resulting in delayed patient treatment. However, this delay would have occurred regardless of device use. Additionally, it is possible physicians could develop an overreliance on the device.
- Failure to identify lesions, potentially resulting in delayed patient treatment, because of software or hardware malfunction. Such malfunctions might include:
 - Incompatibility with hardware and/or data source
 - Inadequate mapping of software architecture
 - Degradation of image quality
 - Prolonged delay of real-time endoscopic video

In all cases of device malfunction, the device may be turned off or unplugged by the colonoscopist or the study team at any time, to avoid further procedural risk, and the procedure would continue as planned without the use of the EVA-C System.

Another risk of this study includes breach of privacy and confidentiality of protected health information (PHI).

The following measures will be implemented to help minimize risks to subjects during the study:

• All PHI will be stored in a secure locked office on a password protected computer. The informed consent forms will be stored in a locked cabinet in a locked office at the site. Measures to ensure complete de-identification prior to data transfer and analysis will be taken.

9. Adverse Events (AE), Serious Adverse Events (SAE), and Unanticipated Problems

During and following a subject's participation in the study, the investigator/institution should ensure that adequate medical care is provided to a subject for any adverse events, including clinically significant laboratory values, related to the trial. The investigator/institution should inform a subject when medical care is needed for intercurrent illness(es) of which the investigator becomes aware.

In the event medical care to a subject is required, the medical care given to, and medical decisions made on behalf of, subjects should always be the responsibility of a qualified physician or, when appropriate, of a qualified dentist.

9.1. Adverse Events

An Adverse Event (AE) is defined as any untoward medical occurrence, unintended disease or injury in subjects, users or other persons, that is considered a change from baseline or pre-study status, whether or not related to the investigational medical device.

Any pre-existing medical condition or symptoms present in a subject will not be considered an AE in this study, unless it worsens as a result of this study.

For this study, AEs related to the study device and study procedures will be reported on an AE Case Report Form and will include the following: Date/time of onset, date the site first becomes aware of the event, description of the event, the duration of the event, the severity of the event, assessment of the relation of the event to the study device and study procedure, description of action taken, if any, and the event outcome.

In the event medical care to a subject is required, the medical care given to, and medical decisions made on behalf of, subjects should always be the responsibility of a qualified physician.

9.2. Serious Adverse Events

A Serious Adverse Event (SAE) is defined as an adverse event that is anticipated or unanticipated and which reasonably suggests that one of the manufacturers' devices has or may have caused or contributed to a death or serious injury.

A Serious Adverse Event is an Adverse Event that led to: (a) death, (b) serious deterioration in the health of the subject that either resulted in a (i) life-threatening illness or injury or (ii) permanent impairment of a body structure or a body function, or (iii) in-patient or prolonged hospitalization or (iv) medical or surgical intervention to prevent life-threatening illness or injury or permanent impairment to a body structure or a body function or (c) fetal distress, fetal death or a congenital abnormality or birth defect.

These events are typically reportable to health authorities. For this study, all serious Adverse Events will be reported to the Sponsor within 24 hours of knowledge of the event.

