Serious Adverse Event	SAE	A Serious Adverse Event (also referred to as Adverse Incident) is defined as an adverse event that is anticipated or unanticipated and that reasonably suggests that one of the manufacturers devices has or may have caused or contributed to a death or serious injury. A Serious Adverse Event is an Adverse Event that led to: (a) death, (b) serious deterioration

VerilyCPR, Protocol, Gastroenterology Artificial INtelligence System for detecting colorectal polyps (The GAIN Study)
Document Number:

		in the health of the subject that either resulted in a (i) life-threatening illness or injury or (ii) permanent impairment of a body structure or a body function, or (iii) in-patient or prolonged hospitalization or (iv) medical or surgical intervention to prevent life-threatening illness or injury or permanent impairment to a body structure or a body function or (c) fetal distress, fetal death or a congenital abnormality or birth defect. These events are typically reportable to health authorities.
Sponsor	N/A	An individual or an organization which takes responsibility for the initiation and/or implementation of a clinical investigation.
Sub-Investigator	Sub-I	A member of the clinical study team with appropriate credentials and is supervised by the Principal Investigator at a site and allowed to perform critical trial-related procedures and/or to make key trial-related decisions.
Subject/ Research Subject	N/A	A human being, either a patient or a non-patient volunteer, participating in a clinical investigation.
Unanticipated Adverse Device Effect	UADE	Serious adverse effect on health or safety or any life-threatening problem or death caused by, or associated with, a device, if that effect or problem was not previously identified in nature, severity, or degree of incidence in the investigational plan or application (including a supplementary plan or application), or any other unanticipated serious problem associated with a device that relates to the rights, safety, or welfare of subjects.

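### Section 9.2 and the Glossary each define a serious adverse event in two non-equivalent ways, one device-linked and one by outcome alone, and do not say which governs

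*Combined protocol and SAP*

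**What the plan says.** Section 9.2 opens by making a suspected device role part of what an SAE is: the event is one that "reasonably suggests that one of the manufacturers' devices has or may have caused or contributed to a death or serious injury". The next paragraph starts again on a different basis: "A Serious Adverse Event is an Adverse Event that led to: (a) death, (b) serious deterioration in the health of the subject", followed by the remaining outcome criteria. That paragraph contains no device link. It builds on the Section 9.1 definition of an adverse event (AE), which applies "whether or not related to the investigational medical device".

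The Glossary entry for SAE has the same structure. It gives the device-linked sentence ("reasonably suggests that one of the manufacturers devices has or may have caused or contributed to a death or serious injury") and then the outcome list. Neither place says that one definition takes precedence, or that both must be met.

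Four other provisions bear on the point:

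- **Capture.** Under Sections 7.2.8 and 9.1, AEs go on the CRF if they are related to the device or to study procedures. Section 7.2.8 adds all SAEs and all unanticipated adverse device effects (UADEs).
- **Escalation.** Section 9.2 requires SAEs to reach the sponsor within 24 hours. Section 9.3 adds reporting to the regulatory authority and review by a Medical Monitor.
- **Device use.** Section 7.2.5 says of control subjects that "the EVA-C System will not be used and will remain turned off during the colonoscopy".
- **Blinding.** Section 7.2.3 states that investigators and site staff know the assignment.

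**The concern.** The two definitions select different events. The outcome list takes in any AE with a serious result. The device-linked sentence takes in only those in which a manufacturer's device is at least suspected of a role. The rule that all SAEs are reported does not settle the matter, because its scope depends on which definition the site has in mind.

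Two things are at stake. The first is reporting: the SAE label triggers the expedited steps, and for a serious event judged unrelated to device and procedure it is also the only route onto the CRF. The second is even-handedness between arms. If the device in question is EVA-C, the label is harder to earn where EVA-C is switched off, and where it is on the label depends on a judgement by someone who knows the assignment. Section 8.3 expects risks much like those of routine colonoscopy. Descriptive SAE counts bear on that expectation only if serious events are labelled alike in both arms.

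**Working it through.** No arithmetic applies. The documents give no SAE rate, no attribution rate and no safety sample size, and they state no figure to reproduce. The check is a comparison of the texts.

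**Step 1: possible readings.** With no rule of precedence, a site can apply the device-linked sentence alone, the outcome list alone, or both together. Requiring both keeps the device link, so for events with a listed serious outcome there are two cases: device link required, or not required.

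**Step 2: classify a serious event by suspected cause.** The table takes the device to be EVA-C and uses the capture rules of Sections 7.2.8 and 9.1.

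| Serious event judged | Device link required | Outcome alone |
|---|---|---|
| Possibly due to EVA-C | SAE | SAE |
| Due to the colonoscopy, not EVA-C | Not an SAE; still on the CRF as a procedure-related AE | SAE |
| Unrelated to device and procedure | Not an SAE; no route to the CRF | SAE |

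The UADE category in Section 9.3 does not rescue the last two rows, because it too concerns problems caused by or associated with a device.

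**Step 3: what is lost.** In the second row the event is recorded, because Section 7.1 lists colonoscopy as a procedure in both arms. It can lose the SAE label, and with it the 24-hour report, the regulatory report and Medical Monitor review. In the third row the event itself may go unrecorded.

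**Step 4: dependence on arm.** With EVA-C off, a control subject would not ordinarily fall in the first row. An intervention subject can, and whether that happens turns on an unblinded attribution. The same complication could therefore be an SAE in one arm and an ordinary AE in the other. This step needs the device to mean EVA-C. Section 11.3 uses the word manufacturer in connection with EVA-C, and Section 11.2 describes no control device, so that reading is natural. The term is nevertheless undefined.

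**Step 5: which definition the rest of the protocol fits.** Section 7.2.1 asks for any SAE among screen failures, who are never randomized and so do not receive the study intervention; that makes sense only under the outcome list. Section 7.1 schedules AE evaluation in both arms. Section 7.2.8 applies relatedness to one reportable group and lists all SAEs as another. Section 9.1 separates the occurrence of an AE from its relation to the device. All four fit the outcome list, and the device-linked sentence is the outlier.

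**The case against.** The strongest reply is that a careful site would not be misled. The outcome list directly follows the device-linked sentence, and Sections 7.1, 7.2.1, 7.2.8 and 9.1 all point to it. This stands in part: it makes universal use of the device-linked sentence unlikely. It does not remove the conflict, which appears in two places with no tie-breaker.

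Three stronger readings are tempting, and the documents do not support them.

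- *No control-arm event could ever be an SAE.* A reader might infer this because EVA-C is off in controls. The sentence, however, sets a threshold of possible contribution and does not require established causation. The devices it refers to are undefined and could be read to include endoscopic equipment used in both arms. Sites may also apply the outcome list.
- *The trial's safety comparison is biased.* The endpoints in Sections 5.3 and 5.4 and the analyses in Section 13 include no safety endpoint or between-arm safety test. Only descriptive counts by arm, if they are tabulated, would suffer.
- *A definite number of SAEs would be missed.* Any count needs an event rate that the documents do not give, for a window that runs only from consent to study exit (Section 7.2.8), with participation of about 1-2 hours and no follow-up (Protocol Summary). Procedure-related events would in any case still reach the AE form.

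**Conclusion.** The point holds as a contradiction between two stated rules, and it is worth correcting. Section 9.2 and the Glossary each carry two SAE definitions that differ in scope, and the label they govern controls expedited reporting, medical review and, for events judged unrelated, whether anything is recorded.

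The consequences are conditional. Loss of the label or of the record requires a site to apply the device-linked sentence. A difference between arms further requires the device to mean EVA-C. Under both conditions, descriptive SAE counts by arm would be unreliable. The size cannot be computed from the documents. The issue concerns clear and consistent safety reporting; type I error, power, the interim analysis and the co-primary endpoints are untouched.

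**What to change.** Reconcile Section 9.2 and the Glossary to a single definition consistent with Sections 7.1, 7.2.1, 7.2.8 and 9.1:

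1. Remove the device-linked sentence in both places.
2. Keep outcome criteria (a) to (c) as they stand.
3. State that the criteria apply in either arm, whatever the relationship to the device or the procedure.
4. Keep relatedness as a separate assessed field, which Section 9.1 already collects.

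The cost is a wording change in two places, a note to sites, and slightly more SAE forms.
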